# HS-2910 Evaluation and Treatment of Pulmonary Vascular Disease in Moderate to Severe Cystic Fibrosis Lung Disease

## 1. Specific Aims

Over time, patients with Cystic Fibrosis (CF) develop disabling lung disease that progresses to chronic respiratory failure, exercise intolerance with marked limitation of physical activity, and premature death. Despite substantial improvements in care, patients with CF often develop pulmonary vascular disease (PVD) that leads to pulmonary hypertension. Previous studies have clearly linked severe pulmonary hypertension and right heart failure with high mortality in CF. Early clinical manifestations of PVD prior to the development of *cor pulmonale* include shortness of breath and dyspnea with exertion, but the extent to which PVD contributes to the decline in exercise tolerance and quality of life in patients with CF is not known. Early evidence of PVD could be recognized in CF patients through standardized exercise testing and echocardiographic evaluation. Identifying those CF patients with PVD prior to the onset of right ventricular dysfunction may allow pharmacologic intervention to attenuate the progression of cardiovascular disease and improve quality of life. Clinical trials have demonstrated that treatment with the phosphodiesterase type 5 inhibitor, sildenafil, can decrease pulmonary vascular resistance and improve exercise tolerance in non-CF patients with pulmonary hypertension. Because experimental and clinical studies have implicated impaired NO-cGMP signaling in the pathophysiology of lung disease in CF, sildenafil may provide a novel pharmacological approach for treating PVD in patients with CF lung disease.

I hypothesize that PVD contributes significantly to exercise intolerance in patients with moderate to severe CF lung disease, and that pulmonary vasodilator therapy will increase exercise capacity, improve cardiac performance during exercise, and enhance quality of life in patients with CF. To test these hypotheses, I propose the following specific aims:

Specific Aim #1: To evaluate the contribution of PVD to exercise intolerance in CF patients with moderate to severe lung disease utilizing cardiac magnetic resonance imaging (MRI), six-minute walk testing (6MWT), cardiopulmonary exercise testing and pulmonary function testing.

Specific Aim #2: To assess whether chronic treatment with the selective pulmonary vasodilator sildenafil citrate will be safe, improve cardiac output, increase ventilatory function, decrease symptoms of exercise intolerance and improve quality of life in CF patients with moderate to severe lung disease.

## 2. Background and Significance

Cystic fibrosis (CF) is the most common life-shortening inherited disease in Caucasians, currently affecting approximately 30,000 people in the United States. Although previously considered a disease of childhood, approximately 50% of U.S. patients are over the age of 18. CF lung disease is characterized by persistent airway inflammation that leads to a progressive decline in pulmonary function and early death.

Even in the setting of early pulmonary disease, exercise intolerance is a prevalent symptom in patients with CF. Additionally, the rate of loss of exercise capacity in patients with CF occurs at a higher rate than in patients without CF. It is known that peak  $\text{VO}_2$  predicts mortality in patients with CF; higher peak  $\text{VO}_2$  is a marker for longer survival.

There are a number of factors that are hypothesized to play a role in exercise intolerance including ventilatory limitation, decreased muscle mass and peripheral muscle dysfunction, and poor nutritional status. It is also possible that Cystic Fibrosis Transmembrane Conductance Regulator (CFTR) gene mutations directly contribute to exercise intolerance. Jiang et al developed mouse models of global CFTR knock out and selective cardiac myocyte knock-out. In both knockout models, mice had increased myocardial contractility, and as well as increased ventricular torsion and strain. They hypothesized that such baseline changes might lead to cardiac remodeling that was independent of lung function. This question has not been explored in patients with CF.

## Pulmonary vascular disease in CF

In addition to abnormalities of the airways, patients with CF who develop significant respiratory impairment are at marked risk for the development of PVD, characterized by pulmonary hypertension (PH) and subsequent *cor pulmonale*. At autopsy, the pulmonary circulation is often characterized by the presence of right ventricular hypertrophy with abnormal muscularization of medium and small pulmonary arteries, with some intimal proliferation and increased extracellular matrix production within the adventitia. With advanced disease, pulmonary artery density is reduced, and subintimal fibrosis and muscularization of pulmonary veins have been noted at autopsy. In addition to these structural changes, past studies have also shown that CF patients have a marked elevation of pulmonary artery pressure with brief exposure to acute hypoxia even in the absence of severe pulmonary hypertension at rest, suggesting that the pulmonary circulation in CF is characterized by abnormal pulmonary vasoreactivity.

Florea et al examined right ventricular (RV) function in 103 adults with severe CF (mean FEV1 20.3 ± 5.3%), and compared their RV function to that of healthy controls. Both RV diastolic and systolic dysfunction were seen in the CF patients. Importantly, while 22 patients had documented pulmonary hypertension (by Doppler echocardiography), only 7 of those patients demonstrated signs and symptoms of overt heart failure. To further assess the prevalence and impact of subclinical pulmonary hypertension (PH) in patients with CF, Fraser et al evaluated cardiac function in 33 adults with moderately severe (FEV1 40-65%, n=13) to severe (FEV1 <40% predicted, n=15) CF lung disease who did not have clinical signs of right heart failure. The authors found no qualitative evidence of RV dysfunction in any of the patients, however 41% of the patients with severe disease, and 20% of those with moderate disease had PH. In a multivariate analysis that included FEV1, awake resting oxygen saturation was found to be the best predictor of pulmonary artery systolic pressure. Importantly, patients with PH had a significantly higher mortality after 5 years than those without PH. In a more recent study, Hayes and colleagues reviewed the United Network of Organ Sharing database to evaluate the effects of mild pulmonary hypertension (mean pulmonary artery pressure greater than or equal to 25 mm Hg as measured on right heart catheterization) on mortality in patients with CF. Both univariate and multivariate Cox models showed increased risk of death even in patients with mild PH (hazard ratio, 1.747; 95% CI 1.387-2.201; P < 0.001; and hazard ratio, 1.757; 95% CI, 1.367-2.258; P < 0.001, respectively).

Mechanisms that contribute to PH and progressive PVD in CF are poorly understood, but are likely due to the long-term effects of inflammation, loss of lung parenchyma and intermittent or prolonged alveolar hypoxia. Although it is clear that patients with more significant lung function impairment are at higher risk for PH, declining FEV1 is not an entirely reliable predictor for the development of PVD in CF. Early clinical manifestations of PVD prior to the development of *cor pulmonale* include shortness of breath and dyspnea with exertion, but the extent to which PVD contributes to these symptoms, and the decline in exercise tolerance and lower quality of life in patients with CF is unknown. Diagnosing PVD in patients with CF prior to overt clinical signs of *cor pulmonale* has historically been difficult as non-invasive evaluation has been limited to echocardiographic estimates of right ventricular (RV) pressure at rest. This diagnostic tool has been shown to underestimate the degree of PVD until significant RV dysfunction has occurred. Identifying CF patients with PVD prior to the onset of significant RV hypertrophy or dysfunction may allow for the earlier application of pharmacologic interventions to improve symptoms and attenuate the progression of disease.

Early evidence of PVD may be recognized in CF patients through standardized exercise testing and echocardiographic evaluation. Abnormal structure and function of the pulmonary vascular bed in CF patients may worsen ventilation/perfusion mismatch, especially during physical activity. Increased pulmonary vascular resistance impedes the normal increase in cardiac output from the RV during exercise, due to the failure to adequately recruit or dilate the distal vasculature, which can lead to more marked rises in pulmonary artery pressure or less ability to increase cardiac output with exercise. With more advanced disease, pulmonary vascular abnormalities become manifest even at rest, leading to increasing strain on the RV, and ultimately, overt RV failure. Early detection would ideally allow for the use of therapeutic interventions to halt the progression of PVD to PH and RV dysfunction, thereby improving the overall quality of life and perhaps survival. Such a treatment strategy would represent a significant improvement over our current approach of awaiting more severe signs of PH with RV failure. Currently, our major approach to the treatment of established pulmonary hypertension is the avoidance of hypoxemia by aggressive monitoring of oxygenation while awake and during sleep, and providing oxygen as needed. Pharmacologic therapies, such as calcium channel blockers, diuretics, and tolazoline have previously been investigated for treatment of PH in CF.

However, these interventions have significant systemic side effects and generally lack long-term benefit, thereby limiting their use. In addition, treatment has generally been initiated late in the clinical course.

### Pharmacologic treatment of PVD

Over the past ten years, new advances in vascular biology have led to remarkable improvements in the clinical care of patients with severe pulmonary hypertension. The use of several interventions, such as prostacyclin analogues, endothelin receptor antagonists, and inhaled nitric oxide (NO), have led to increased survival in patients with idiopathic and secondary causes of PH. Extensive studies in diverse animal models have implicated disruption of NO-cGMP signaling as a major factor in the abnormal vascular tone, reactivity and structure in development of PH. Increased activity of the cGMP specific phosphodiesterase type 5 (PDE5) isoform in vascular smooth muscle inactivates cGMP, thereby worsening vasoconstriction, smooth muscle cell proliferation and adventitial growth.

Inhibition of phosphodiesterase type 5 (PDE-5,) which is responsible for degradation of cGMP, or stimulation with nitric oxide (NO) can cause protein kinase G-dependent smooth muscle relaxation. Sildenafil-induced increased cGMP concentration leads to pulmonary vasculature smooth muscle relaxation, and it is this effect that is key in treatment of pulmonary hypertension. Sildenafil citrate is FDA-approved for treatment of pulmonary hypertension, and has been used to treat both adult and pediatric patients with pulmonary hypertension. In a large trial of sildenafil use for pulmonary hypertension, escalating doses of sildenafil were used for 12 weeks. Although the initial group of subjects was treated for 12 weeks, improvements in the primary outcome were seen at 4 weeks. Whether sildenafil therapy can improve pulmonary hemodynamics at rest and during exercise, and enhance the quality of life in patients with CF have not been studied.

In addition to its potential effects on the pulmonary circulation, sildenafil may potentially improve lung function in CF patients through other mechanisms effected by the NO-cGMP signaling cascade. Several studies have shown that endogenous production or bioactivity of NO is markedly impaired in the airways of patients with CF. Animal and clinical data have shown marked down regulation of inducible NO synthase (NOS) in airway epithelium, strong associations of severe lung disease with endothelial NOS polymorphisms, and increased degradation of NO metabolites, and decreased amounts of NO in exhaled breath condensate of patients with CF. Thus, CF lung disease can be characterized by a relative NO deficiency with down-regulation of the NO-cGMP signaling cascade.

Although the exact role of NO signaling in the CF airway is unclear, several studies have suggested that the NO-cGMP cascade plays an important role in airway inflammation and bacterial infection. Sildenafil has also been shown to have anti-inflammatory effects. For example, Toward et al demonstrated that pretreatment with sildenafil inhibited LPS-induced airway hyper reactivity, white cell influx and NO dysfunction in two guinea pig models of airway disease. In CF respiratory epithelial cells, Poschet et al demonstrated that the excessive pro-inflammatory response to *P. aeruginosa* exposure could be reversed by treatment with sildenafil. Based on the *in vitro* data suggesting a possible role for PDEi as anti-inflammatories in CF, I designed a single site open-label dose escalation study (Clinicaltrials.gov No.: NCT00659529) to evaluate the safety, efficacy and pharmacokinetics of sildenafil in subjects with mild to moderate CF lung disease. On study day 1, subjects underwent exhaled breath condensate (EBC) measurement, lung function and routine laboratory testing, completed the CF Health Related Quality of life questionnaire (CFQ-R), and had sputum collected for bacterial counts and sputum biomarkers. Subjects received oral sildenafil 20 or 40 mg p.o. t.i.d. for 6 weeks, and all evaluations were repeated at the end of 6 weeks. Twenty subjects completed the study. There were no drug-related serious adverse events, and side effects were generally mild and consistent with those previously reported. There was improvement in the primary endpoint, mean sputum elastase ( $p < 0.03$ ), which is a sensitive measure of CF airway inflammation and has been shown to predict lung function decline in patients with CF. There was also a non-significant trend towards improvement in sputum IL-8 ( $p = 0.13$ ). There was no difference in EBC pH, the respiratory score of the CFQ-R, or sputum microbiology ( $p = 0.44, = 0.88$  and  $1.0$ , respectively). With recent data showing a correlation between systemic markers of inflammation and pulmonary artery pressure in adults with CF, this aspect of sildenafil therapy may also be important in patients with advanced disease.

One final aspect of PDEi therapy that may be important in CF is its effect on CFTR function. Recent studies have also shown that PDEi can potentiate CFTR-mediated chloride transport activity and also correct surface

#### 4. Research Design and Methods

##### A. Study Design

This study is blinded pilot study that examines the use of sildenafil citrate in clinically stable patients with moderate to severe CF lung disease. Subjects will be randomized in a 3:1 (sildenafil:placebo) fashion. Subjects will perform exercise, pulmonary function and quality of life evaluations before and after 12 weeks of

therapy with sildenafil or placebo. The length of participation for each subject will be approximately 16 weeks, and will consist of a screening visit, three clinical evaluations and four phone evaluations over the study period.

## B. Patient Population

Twelve clinically stable adult CF patients  $\geq$  to 18 years of age will be recruited and enrolled from the adult outpatient CF clinic at NJH. Additional subjects (up to 20) may be enrolled if any patient leaves the study. We expect to enroll an approximately equal number of males and females. Most CF patients in the Colorado CF clinics are of white, non-Hispanic origin and I anticipate this ethnic mix to persist in this study. Because sildenafil has not been formally studied in CF patients with moderate to severe CF lung disease, and it is now uncommon for children to develop severe disease I will limit enrollment to adult patients for this pilot study.

## C. Inclusion and Exclusion Criteria

### *Inclusion Criteria*

- 1) Confirmed diagnosis of CF based on the following criteria: Positive sweat chloride  $\geq 60$  mEq/liter (by pilocarpine iontophoresis) and/or Genotype with two identifiable mutations consistent with CF, and accompanied by one or more clinical features consistent with the CF phenotype
- 2) Male or female patients  $\geq$  18 years of age
- 3) FEV1  $\geq$  20% predicted and  $\leq$  70% predicted (Hankinson)
- 4) Clinically stable without evidence of acute upper or lower respiratory tract infection or current pulmonary exacerbation within the 14 days prior to the screening visit
- 5) Ability to reproducibly perform spirometry (according to ATS criteria)
- 6) Ability to understand and sign a written informed consent or assent and comply with the requirements of the study
- 7) Willingness to maintain chronic CF medication schedule (e.g. alternating month inhaled antibiotics)

[figure not shown]
### *Exclusion Criteria*

- 1) History of hypersensitivity to sildenafil
- 2) Use of an investigational agent within the 4-week period prior to Visit 1 (Day 0)
- 3) Breastfeeding, pregnant, or verbal expression of unwillingness to practice an acceptable birth control method (abstinence, hormonal or barrier methods, partner sterilization or intrauterine device) during participation in the study for women of child-bearing potential.
- 4) History of significant hepatic disease (AST or ALT  $>$  3 times the upper limit of normal at screening, documented biliary cirrhosis, or portal hypertension),
- 5) History of significant cardiovascular disease (history of aortic stenosis, coronary artery disease, or life-threatening arrhythmia),
- 6) History of severe neurological disease (e.g. history of stroke),
- 7) History of severe hematologic disease (e.g. history of bleeding diathesis; current INR  $>$  2.0)
- 8) History of severe ophthalmologic disease (e.g. history of retinal impairment or non-arteritic ischemic optic neuritis)
- 9) History of severe renal impairment (creatinine  $>$ 1.8 mg/dL.)
- 10) Inability to swallow pills
- 11) Previous organ transplantation
- 12) Use of concomitant nitrates,  $\alpha$ -blocker, or Ca channel blocker (currently or within one month of Visit 1)
- 13) Use of concomitant medications known to be potent inhibitors of CYP3A4 [e.g. ketoconazole, itraconazole, ritonavir, clarithromycin, erythromycin, rifampin (currently or within one month of initiation of study drug)] NOTE: use of azithromycin is NOT a cause for exclusion
- 14) History of sputum or throat swab culture yielding *Burkholderia cepacia* or *Mycobacteria massiliense* within 2 years of screening
- 15) Weight less than 40 kg at Screening
- 16) History of migraine headaches.
- 17) Resting room air oxygen saturation  $<$ 80% without supplemental oxygen
- 18) Presence of a condition or abnormality that in the opinion of the investigator would compromise the safety of the subject or the quality of the data
- 19) Start of CFTR modulator therapy less than 1 month prior to first dose of sildenafil or placebo
- 20) Use of anticoagulants

Frank pulmonary hypertension (RVSP >40 mmHg by ECHO)

D. Study visits

### Study Timeline

*Screening visit (Day -14-0):* Prior to conducting any study-related activities, written informed consent/assent will be obtained, signed and dated by the subject. A medical history including diagnosis of CF, current medications and other relevant past medical history will be obtained, and a complete physical exam will be performed by a study investigator. Height, weight, temperature, blood pressure, respirations and baseline pulse oximetry will be recorded. Any abnormal findings will be documented. An ECG and an ECHO will be done. Routine laboratory studies will be performed. Because sildenafil citrate is a class B drug, a urine pregnancy test will be performed for females of child-bearing potential. Female enrollees will be counseled to utilize appropriate contraceptive methods while participating in this study. Subjects will undergo spirometry according to ATS criteria.

*Study visit 2 (Day 1):* Subjects meeting entry criteria will be evaluated in the outpatient research unit. CFQ-R (see description below) will be administered prior to all other assessments. Vital signs will be obtained. A physical exam will be performed by a study investigator. Routine laboratory studies will be performed. Sweat test will be performed. Complete lung function will be performed. Cardiac MRI will be performed to classify subjects' estimated right heart pressures and right heart function. After completing spirometry and baseline MRI examination, a six-minute walk test and cycle ergometry test will be performed (see description of each procedure below). Tests will be performed in that order. Subjects will have a 30 minute rest period between the six-minute walk and the CPET. Subjects will be educated on the use of the fitbit. At the completion of the visit, each subject will begin daily treatment with sildenafil citrate or placebo (Belmar Pharmacy) at an oral dose of 20 mg, three times daily. Blood pressure will be checked at 30 minutes, 1 hour, and 2 hours after the first dose.

*Study visit 3 (Day 7±3):* After 7 days of therapy, the subject will return to the study site for vital signs, review of concomitant medications, and discussion of concerns related to sildenafil therapy. If tolerated (see **Subject and Study Stopping Criteria**), the oral sildenafil or placebo dose will be increased to 40mg, three times daily. If there is evidence of sildenafil intolerance (blood pressure will be checked at 30 minutes, 1 hour, and 2 hours after the first increased dose), the dose will be decreased to the previous dose or discontinued. If sildenafil is

discontinued, the patient will be removed from the study. Oral sildenafil therapy will continue at 40mg, three times daily for eleven weeks. (Total sildenafil or placebo therapy will last twelve weeks.)

*Phone contact 1 (Day 28±3):* Phone contact will be made with each subject to review dosing, compliance and side effect profiles. Phone contacts will be recorded on case report forms.

*Study visit 4 (Day 42±3):* The subject will return to the study site for CFQ—R vital signs, review of concomitant medications, and discussion of concerns related to sildenafil therapy. A study investigator will perform a brief physical exam. The subject will perform spirometry and will complete a 6MWT.

*Study visit 5 (Day 84±3):* Subjects will return to the outpatient research unit, where the CFQ-R (see description below) will be administered prior to all other assessments. A physical exam will be performed by a study investigator. Vital signs, weight, safety labs, and urine pregnancy in all women, will be done. Spirometry will be performed. Sweat test will be performed. After completing spirometry, cardiac MRI will be performed, a six-minute walk test and cycle ergometry test will be performed (see description of each procedure below). Tests will be performed in that order. Subjects will have a 30 minute rest period between the six-minute walk and the cycle ergometry test. The fit-bit will be removed. At the conclusion of this visit, subjects will be instructed to discontinue sildenafil or placebo therapy.

*Phone contact 2 (Day 98±3):* The study coordinator will call to review adverse events and concomitant medications. If there are new abnormalities or changes in medication felt to be study-related, these abnormalities will be followed up with weekly visits to the study site until resolution.

*Exacerbations:* During the course of the study, any enrolled subject requiring hospitalization and/or intravenous antibiotics for a cystic fibrosis-related pulmonary exacerbation will be withdrawn from the study.

*Early Withdrawal:* In case of early withdrawal, an Early Withdrawal Visit will be scheduled within 7 days following the last dose of study medication. Unless medically contraindicated, CFQR, safety labs, serum pregnancy for all women, spirometry, a six-minute walk test and cycle ergometry test will be performed. Physical exam will be performed by a study investigator including weight, temperature, blood pressure, respirations and pulse oximetry. Any abnormal findings will be documented. All remaining study drug will be collected.

*Concomitant medications:* All subjects should continue the same medications throughout the study period, as medically feasible, with no introduction of new chronic therapies during or <4 weeks prior to enrollment. If a change in concomitant medications is required, the reason(s) for the change(s) will be recorded on the subject's CRF.

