### E. Outcome measures

Clinical laboratory tests will be performed including complete blood count with differential, comprehensive chemistry profile [including sodium, potassium, bicarbonate, blood urea nitrogen, creatinine, alanine aminotransferase (ALT), aspartate aminotransferase (AST), alkaline phosphatase, and total bilirubin) PT/INR, and serum pregnancy test (for females of child-bearing potential) will be performed at the screening and end of study visits for safety. Add HS-CRP

*Assessment of lung function:* Spirometry will be performed at the screening and end of treatment visits by a CF research coordinator according to ATS standards.

*Assessment of health related quality of life:* The CFQ-R, which has been shown to correlate with survival in CF, is designed to measure CF-specific patient-reported health-related quality of life. The 48 questions encompass five domains including physical symptoms, role functioning (e.g. school/work), psychological and emotional functioning, energy/fatigue, and social functioning. The four domains specific to CF that are measured are: eating disturbances, body image, embarrassment caused by symptoms, and treatment burden. This questionnaire has been validated in CF patients. The questionnaire will be administered at the first, interim and end of treatment visits.

*ECHO:* Echocardiogram will be performed at the screening visit to insure that the subject does not meet the exclusion criterion of frank pulmonary hypertension.

*Six Minute Walk Test:* 6MWT will be performed according to ATS standards.

*Cardiac MRI:* Cardiac MRI is a non-invasive imaging method to evaluate pulmonary artery blood flow and right heart structure and function. Pulmonary artery blood and right heart structure and function will be measured before and after treatment with sildenafil or placebo.

*Fitbit monitoring:* In order to determine whether sildenafil improves exercise tolerance on a day-to-day basis, subjects will wear a Fitbit for the 12 weeks of the study for monitoring.

*Sweat test:* Pilocarpine iontophoresis will be performed and sweat collected according to CFF standards. Sweat volume will be recorded. Sweat will be collected using the Macroduct® collection system. Samples will be shipped to the TDN Core laboratory in Aurora, CO for chloride concentration measurement.

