### Pregnancy

If a subject becomes pregnant during the study, the subject will be discontinued from the study.

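### Pregnancy is an exclusion, but the only pregnancy test scheduled before dosing is at screening, so the first dose can rest on a negative result 1 day to at most 15 days old

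*Combined protocol and SAP*

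**What the plan says.** Exclusion criterion 3 (section 4.C) begins: "Breastfeeding, pregnant, or verbal expression of unwillingness to practice an acceptable birth control method".

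Under Study Timeline (section 4.D), screening may fall anywhere from Day -14 to Day 0. The pregnancy test is placed there: "Because sildenafil citrate is a class B drug, a urine pregnancy test will be performed for females of child-bearing potential". Contraceptive counselling follows at the same visit.

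Visit 2 is Day 1. Its text lists routine laboratory studies but no pregnancy test, and ends: "At the completion of the visit, each subject will begin daily treatment with sildenafil citrate or placebo".

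The schedule table (under DMC) marks the pregnancy test at Screening, End of study and Early Term, and leaves Visit 2 blank. The laboratory row, which is marked at Visit 2, lists CBC, liver function, chemistry, INR and CRP.

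On the type of test the text is divided:
- The Study Timeline has urine at screening (as quoted above) and at Visit 5: "urine pregnancy in all women, will be done".
- The Early Withdrawal paragraph has "serum pregnancy for all women".
- Section E, Outcome measures, has "serum pregnancy test (for females of child-bearing potential) will be performed at the screening and end of study visits for safety".

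If a pregnancy is recognised later, the Pregnancy section applies: "If a subject becomes pregnant during the study, the subject will be discontinued from the study". Pregnancy is also listed among the criteria for stopping study drug.

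**The concern.** An exclusion criterion protects participants only as far as it is checked before exposure. Here the check may precede the first dose by up to about two weeks, and the plan sets no maximum age for the screening result. A pregnancy too early to detect at screening, but detectable on Day 1, would be dosed although criterion 3 was meant to keep that woman out. Blood counts, chemistry and INR are repeated at Visit 2 before dosing; the test behind the pregnancy exclusion is not.

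The stake is participant safety in a small number of women. Nothing in the endpoints or the analysis depends on it.

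**Working it through.** **1. Check on the screening window.** Study Design (section 4.A) gives about 16 weeks of participation per subject. The last contact is nominally Day 98. From Day -14: 98 - (-14) = 112 days = 16.0 weeks. This agrees with the stated length and supports Day -14 as a permitted screening day.

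**2. Age of the negative result at first dose** = Day 1 - screening day.
- Screening on Day 0, the label that Exclusion criterion 2 and the schedule table give to Visit 1: 1 - 0 = 1 day.
- Screening on Day -14, the earliest day the Study Timeline permits: 1 - (-14) = 15 days.
- With a test at Visit 2 before dosing: 0 days.

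**3. Is a Visit 2 test implied elsewhere?** The sentence on routine laboratory studies also appears at screening, where the pregnancy test is named separately. The schedule's laboratory row does not include it. Section E points the same way but is weak support: it gives one timing, screening and end of study, for the whole laboratory panel, while the Study Timeline and the schedule also put laboratory work at Visit 2. The point rests on the Study Timeline and the schedule, which are enough.

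**4. Which conceptions a Visit 2 test would newly detect.** Let S be the screening day and L the days from conception until a test turns positive (not given; it cancels). Screening detects conceptions before S - L; a Visit 2 test detects those before 1 - L. The newly covered window is (1 - L) - (S - L) = 1 - S, that is 1 to 15 days. With L = 14 (assumed) and S = -14 it runs from Day -28 to Day -13, nearly all of it before screening and its counselling.

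**5. Number of tests.** Section 4.B expects roughly equal numbers of men and women among 12 subjects, and adds: "Additional subjects (up to 20) may be enrolled if any patient leaves the study". Reading 20 as the total and counting every woman as of child-bearing potential: 12 × 0.5 = 6; 20 × 0.5 = 10.

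**6. Yield, as an upper-bound illustration.** The documents give no conception rate. Suppose every woman is screened on Day -14, and spread a monthly conception probability p evenly over 30 days. One expected newly detected pregnancy needs:
- 6 women: 6 × (15/30) × p = 1, so p = 0.33.
- 10 women: 10 × (15/30) × p = 1, so p = 0.20.

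With 3:1 allocation only three quarters of these women would receive sildenafil. One expected active-drug exposure prevented needs:
- 6 women: p = 1/(6 × 0.5 × 0.75) = 0.44.
- 10 women: p = 1/(10 × 0.5 × 0.75) = 0.27.

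**7. What the test would not change.** After Day 1 the next scheduled test is at Visit 5, Day 84±3 (Day 81 to 87), which is 80 to 86 days after the first dose. A Visit 2 test leaves that interval as it is.

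**The case against.** The strongest reply is that this is a preference. The plan layers its controls: exclusion of pregnant women and of those who say they will not use contraception, a screening test, counselling, and discontinuation once a pregnancy is known. It ties the testing to the drug's pregnancy class. Nothing in the documents requires a same-day test. This stands, and it is why the point is offered as an improvement only. The controls lower the risk but do not detect a pregnancy that began before screening and was not yet detectable there.

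Three stronger readings are tempting, and the documents do not support them.
- A reader might infer that the plan breaks its own rule by dosing without a current test. It sets no such rule, and a test within 14 days is coherent with the exclusion.
- A reader might take 15 days as the usual gap. It is the permitted maximum. Two places label Visit 1 as Day 0, and nothing shows how early screening normally happens.
- A reader might infer from the mixed assay wording that serum in section E is a mistake for urine. The text splits two and two, so it does not settle which was meant.

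It is also fair to say that the longer untested stretch comes after dosing starts, and that this change does not touch it. That limits the benefit. It does not remove it, because the gap addressed here lies before any exposure.

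**Conclusion.** The point holds as a low-cost participant-safety improvement, worth considering. The first dose can follow a negative test by 1 day to at most 15 days, and a Visit 2 test would bring that to zero. This follows directly from the visit days and needs no assumption.

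The yield does rest on assumptions: equal sexes, all women of child-bearing potential, every woman screened on the earliest day, and conceptions spread evenly over a 30-day month. Even so, one expected detection would need a monthly conception probability of 20% to 33%. In women who have not refused contraception the expected number is taken to be well below one, though the documents give no rate from which to state it. The case for acting is therefore the very low cost, not the expected count. There is no bearing on endpoints, sample size or analysis.

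**What to change.** Add a urine pregnancy test for women of child-bearing potential at Visit 2, with a negative result required before the first dose. Enter it in the Visit 2 text of the Study Timeline and in the Visit 2 cell of the schedule's pregnancy row.

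Cost: about 6 tests, or about 10 if enrolment reaches 20, at a visit that already takes samples and with a test the Study Timeline already uses. It can follow the CFQ-R, which must come before all other assessments. The schedule marks randomization at screening, so a positive result could leave a randomized subject undosed; section 4.B allows additional subjects when someone leaves. A conception too recent to detect on Day 1 would still be missed.

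As a separate editorial matter, the sponsor should state which assay is intended at screening, end of study and early withdrawal, and make the Study Timeline and section E agree. The Visit 2 test does not depend on that answer.
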